1.3.1 Potential Risks

Hand-held pulse oximeter:

The pulse oximeter is a non-invasive diagnostic device intended to measure systematic blood oxygenation and pulse rate. In this study, we will use a portable pulse oximeter (CMS60D) to measure blood flow in the tooth pulp. Clinical decisions will not be based on the results obtained from this test. The signal emitted from the sensor is light, and there is little to no risk associated from the pulse oximeter to human tissue. The pulse oximeter is battery operated and the sensors are isolated in plastic sheaths.

Infection control measures will be implemented for all items entering the oral cavity. The pulse oximeter sensors will be cleaned with disinfecting wipes (Colorox Healthcare Hydrogen Peroxide Cleaner Disinfectant, Colorox Company, Latham, NY) and then individually wrapped with a latex free, translucent, elastic barrier (CurelasticTM, Steri-Shield Products, Las Vegas, NV). The insulated wiring harness that connects the sensors to the body of the pulse oximeter will also be cleaned with disinfecting wipes and then covered with a barrier film (Universal Cover Barrier, Patterson Dental, Saint Paul, MN). A custom made sensor holder will be used to hold the pulse oximeter sensors onto the teeth (see below for additional details). The sensor holder will be cleaned with disinfecting wipes prior to use.

A new set of sensor holder will be used for each individual patient. We will plan to re-use the sensors total of 1-2 times. At each time, then sensors and its connecting wires will be wiped using

alcohol wipe and then covered using protection barrier, "blue tape". After each use, the blue tape would be removed and the sensors and its connectors be wiped again with alcohol

Laser Doppler Flowmeter (LDF):

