1.3.2 Potential Benefits

Participants are not expected to receive any personal benefits from being in this study.

OBJECTIVES

1.4 **Study Objectives**

The purpose of this study is to assess tooth health by using a pulse oximeter which measures the blood flow within the tooth. We hypothesize that if we can measure both sensation and blood flow in a tooth, we will be able to better determine if the tooth is "alive or dead". In the future, this method may help determine which teeth are diseased and require dental treatments.

Our specific aims are:

Aim - 1: To measure pulpal blood flow using pulse oximeter and Laser Doppler Flowmeter

Aim - 2: To measure tooth vitality using Cold, Electrical Pulp tester (EPT) , percussion and palpation testing

Aim - 3: To assess histological presentation of the pulp the extracted teeth

Aim - 4: To evaluate the relationships between the Aims 1-3 to determine if pulpal blood flow is a reliable indicator of tooth vitality.

1.5 **Study Outcome Measures**

Primary Outcomes Measures: Correlation Between Subjective and Objective Measurements of Pulpal Status

- Subjective Measurements Pulpal Status: Conventional pulpal diagnosis using cold test [Endo Ice, Coltene/Whaledent, Cuyahoga Falls, OH, USA] and Electrical Pulp Test -EPT S[Kerr Vitality Scanner, SybronEndo] testing and recorded, along with vertical and lateral percussion and palpation responses. Conventional pulpal diagnosis assessment would be used for teeth that are planned for extraction and additional teeth (10 total) in each participant
- *Objective Measurements Pulpal Status:* Measurements obtained from pulse oximeter gives a series of reading of oxygen saturation level, and pulse. Pulse oximeter measurements would be used for teeth that are planned for extraction and also up to 2-5 additional teeth in each participant

Exploratory Outcomes:

- *Systemic Vital Sign Measurements:* Blood pressure and pulse recording will be obtained from the recorded values from the participant's chart.
- *Histological Assessment of the Extracted Teeth:* Upon completion of extraction, the teeth will be placed in formalin-containing bottle. After formalin fixation, the teeth will be prepared for histological examination using 10% EDTA for demineralization. Following that, the teeth are trimmed, embedded in paraplast and cut longitudinally to obtain 6um thick section. The sections were stained with H&E and examined with a light microscope.

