- *Laser Doppler Flowmeter (LDF):* Measurements obtained from LDF pulse oximeter gives a series of reading of blood velocity. LDF measurements would be used for teeth that are planned for extraction and also up to 2-5 additional teeth in each participant

STUDY DESIGN

Standard Care Procedures:

Participants may receive the following treatment procedures whether he/she join this study or not:

- Review of medical and dental history
- Oral examinations
- Dental Procedures (e.g., extractions) planned by his/her oral surgery provider

Study-Related Procedure

- The researcher will gather information initially by asking if any of the teeth are hurting or sensitive to hot/cold
- Participants will complete self-report questionaries' regarding their history of dental pain
- Existing panoramic radiograph will be reviewed by a member of research team prior to choosing which teeth (less than 10) will be to be tested.
- Blood pressure, and heart rate values would be recorded on this appointment from your medical record by a member of research team prior to the extraction.
- The researcher initially will palpate the gum around selected teeth and record any discomfort
- A plastic clip, pulse oximeter will be placed over the teeth, one at a time, to measure blood flow by measuring the presence of pulse in these teeth for approximately for 15-30 seconds.
- The clip will remain on the tooth for additional 2-3 minutes to continually measuring pulse while the following tests are taken place:
 - **Cold Testing**: This test is used to assess if the tooth is "dead" or "alive" by measuring sensation of cold from the tooth. A small cotton ball will be sprayed with cold spray (called Endo-Ice) and then placed on the surface of that tooth for approximately 15 seconds or till participant reports any sensation of cold. There would be 30 seconds wait time prior to the next step.
 - **Electrical Pulp Testing:** This test is used to assess if the tooth is "dead" or "alive" by measuring sensation of electrical pulses from the tooth. A small probe attached to an electrical pulp testing (EPT) device will be placed on the surface of that tooth for approximately 15 seconds or till participant reports any tingling sensation. There would be 30 seconds wait time prior to the next step.

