1.22 Final Analysis Plan

To compare accuracy of pulp vitality between traditional tooth vitality testing (Cold and EPT) to pulse oximeter reading to determine if the pulse oximeter is a reliable indicator of tooth vitality. We will analyze the relationships between these clinical readings using Pearson correlations and/or Chi Square tests. We will evaluate repeatability of the measurements within a tooth for the pulse oximeter using Bland-Altman plots, intraclass correlation coefficients (ICCs), and the percentage of repeat measurements within +/- 0.5 mm along with a 95% confidence interval for the percentage. Pulse oximeter reading will be compared against the gold standard (Cold and EPT) assessment using paired t-tests, 95% confidence intervals for the difference from the gold standard with a 95% confidence interval. The clinical pulpal status will be compared to the histological status for the difference using ANOVA and compared for the percentage of measurements with +/- gold standard visual assessment of the pulp status using McNemar's tests.

SOURCE DOCUMENTS AND ACCESS TO SOURCE DATA/DOCUMENTS

Study staff will maintain appropriate dental and research records for this study. Study staff will permit authorized representative and regulatory agencies to examine (and when required by applicable law, to copy) research records for the purposes of quality assurance reviews, audits and evaluation of the study safety, progress and data validity.

QUALITY CONTROL AND QUALITY ASSURANCE

Quality control will be continually monitored by periodic (semi-annual) reviews of the protocol and procedures used in the study. All questionnaire data is reviewed on the day of the participant visit for completeness. De-identified data is monitored after collection for various points of quality assurance.

ETHICS/PROTECTION OF HUMAN SUBJECTS:

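### The tolerance for repeat pulse oximeter readings is in millimetres, a unit the device does not report, and section 1.22 does not say which readings are the repeats

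*Combined protocol and SAP*

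**What the plan says.** Section 1.22 (Final Analysis Plan) assesses within-tooth repeatability of the pulse oximeter in three ways: Bland-Altman plots, intraclass correlation coefficients (ICCs), and "the percentage of repeat measurements within +/- 0.5 mm along with a 95% confidence interval for the percentage".

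Two sections describe what the device reports. Section 1.3.1 says: "The pulse oximeter is a non-invasive diagnostic device intended to measure systematic blood oxygenation and pulse rate". Section 1.5 (Study Outcome Measures) says: "Measurements obtained from pulse oximeter gives a series of reading of oxygen saturation level, and pulse". The Study Design section describes the opening step differently: the clip is placed "to measure blood flow by measuring the presence of pulse in these teeth for approximately for 15-30 seconds".

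That section and the Schematic of Study Design then keep the clip in place for a further 2-3 minutes of continual pulse measurement. Cold, electrical pulp testing (EPT) and percussion are done in that time, with a 30 s wait after each. The clip is then taken off and refitted with the laser Doppler sensor. Form 2 has one Pulse Ox row per tooth.

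**The concern.** There are two separate faults.

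- **Unit.** A limit in millimetres cannot be applied to a saturation in per cent or a pulse rate in beats per minute. It cannot be read as a simple slip with an obvious correction either. The device has two outputs in different units, and nothing shows which quantity or limit was meant. A limit chosen after the data are seen would let the result set its own standard.
- **Repeats.** Bland-Altman and ICC have no unit problem for numeric readings, but they need a defined pair. Section 1.22 gives no number, timing or spacing of readings. If one reading precedes a stimulus and the other follows it, any pulpal or systemic response is counted as device error, and repeatability looks worse than it is. Two readings taken very close together could make it look better than it is.

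At stake is whether the repeatability results can be interpreted. That matters because the protocol adapts a device normally used on skin to teeth, in a custom holder (section 1.3.1).

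**Working it through.** **1. Units side by side.** No derivation of the 0.5 mm figure is given, so there is nothing to reproduce.

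| Place | Quantity | Unit |
|---|---|---|
| 1.22 | tolerance for repeats | mm |
| 1.3.1 | blood oxygenation, pulse rate | not a length |
| 1.5 | oxygen saturation, pulse | not a length |
| Study Design | presence of pulse | yes/no as worded |
| Form 2 | Pulse Ox | none stated |

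No conversion to a length is given. The only other millimetre figure found is the 5-8 mm silicone layer of the sensor holder in 1.3.1, which is not a measurement. The percentage within tolerance is therefore undefined, and so is its interval.

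**2. Where the repeats could come from.** The procedures give one oximeter placement per tooth; the second placement carries the laser Doppler sensor. Any oximeter repeats must come from the single recording.

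- Total length: 15 + 120 = 135 s to 30 + 180 = 210 s.
- Share before any test, lowest: 15 / (15 + 180) = 15/195 = 7.7%.
- Share before any test, highest: 30 / (30 + 120) = 30/150 = 20.0%.

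The rest spans the three tests and their waits. Readings picked from the whole series without a rule could easily fall on opposite sides of a stimulus.

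**3. Illustration of the confidence interval once a tolerance exists.** This does not measure either fault. It shows why the interval must allow for several teeth per participant. Assumptions, none from the documents except where stated:

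- 90% of pairs within tolerance, and one valid pair per tooth.
- One extracted tooth plus 2 to 5 others (the 2-5 is from the oximeter item in 1.5), so m = 3 or 6 teeth.
- All 35 completers (section 1.21) contribute.
- Within-participant correlation r of 0.1 to 0.5.

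Independent half-width = 1.96 × √(0.90 × 0.10 / n). Clustered half-width = that × √(1 + (m − 1)r).

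| Teeth m | Pairs n | Independent | Design effect | Clustered |
|---|---|---|---|---|
| 3 | 35 × 3 = 105 | 5.7 points | 1.2 to 2.0 | 6.3 to 8.1 points |
| 6 | 35 × 6 = 210 | 4.1 points | 1.5 to 3.5 | 5.0 to 7.6 points |

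**The case against.** The strongest reply is that repeats are planned. Section 1.5 speaks of a series of readings, the clip records for a further 2-3 minutes, and the reading column in the first block of Form 2 is headed in the plural. That stands. A reader might infer from the single Pulse Ox row that no repeat readings exist, and the documents do not support this: one row does not prove one reading. The readings are under-specified, not absent.

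A reader might also infer that most of the recording is contaminated by stimulation. The documents do not support that either. Cold and EPT last about 15 s each, or less if the participant responds. Percussion is a gentle tap with no stated duration. Each test is followed by a 30 s wait. Neither the time under stimulus nor any carry-over into the waits can be bounded from the text.

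Nor should the illustration be stretched to ten teeth. The phrase "additional teeth (10 total) in each participant" belongs to the conventional tests, not the oximeter, and it conflicts with the Study Design wording, "prior to choosing which teeth (less than 10) will be to be tested".

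The presence-of-pulse wording sits in a lay-style procedure list, while section 1.5 is the outcome definition, so numeric readings are the likelier intention. Section 1.34 mentions a Manual of Procedures, which is not among the documents. It might fix reading times, but 1.22 does not refer to it, and it could not make millimetres valid.

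Finally, repeatability is neither a numbered aim nor a listed outcome. That limits the weight of the point but does not answer it.

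**Conclusion.** The point holds, within limits. The unit fault is certain: one of the three planned repeatability results cannot be computed as written. The undefined repeats are a lesser fault of specification, and they affect the other two results as well. The size of any bias from pairing across a stimulus is unknown. The 7.7% to 20.0% figure shows only how little of the recording precedes every test. The half-widths in the illustration depend wholly on the assumed 90% agreement, correlation and tooth counts.

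A reader might infer that the main result is compromised. It is not. Section 1.5 gives "Primary Outcomes Measures: Correlation Between Subjective and Objective Measurements of Pulpal Status", and that analysis uses neither the tolerance nor the repeat pairs. Repeatability is a supporting analysis. The correction is worth making because it is cheap and because the limit should be fixed before the data are analysed.

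**What to change.** 1. In 1.22, name the quantity analysed and replace the millimetre limit with a tolerance in its own unit: SpO2 percentage points, beats per minute, or one for each. Give the reason for the value and fix it before the data are analysed. If only presence or absence of pulse is recorded, report percentage agreement instead, since Bland-Altman and a numeric tolerance would not apply.
2. Define the repeats as two readings at named times in the opening window before the cold test, the same for every tooth, and record both on Form 2. The documents do not give the device's averaging interval, so check that the window can hold two separate readings. If it cannot, take the second at a named time late in one named 30 s wait, and report that carry-over may be included.
3. Base the Bland-Altman plots, the ICC and the percentage on those two readings. Compute confidence intervals that allow for several teeth per participant, for example with a bootstrap that resamples participants. Describe the result as within-placement repeatability.

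The cost is a few sentences in 1.22, one extra Form 2 field per tooth, and IRB approval of the amendment (section 1.24). Both readings come from the recording already planned, so no extra recording is needed. For any tooth measured before the change, a second reading may not be recoverable.

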- **Objectives:** The objective of this study is to evaluate if pulse oximeter measurements are a reliable marker for patient's reported symptoms and/or histological evaluations.
- **Population:** 35 participants

Site: University of Michigan, Ann Arbor MI

Study Duration: 24 months

Subject Participation Visit 1: approximately 45 minutes **Duration:**

Estimated Time to 6 months **Complete Enrollment:**

Schematic of Study Design:

	Study-Rel	ated Procedure
	1)	The researcher will gather information initially by asking if any of the teeth are hurting or sensitive to hot/cold
	2)	Participant will complete self-report questionaries' regarding their history of dental pain
	3)	Existing panoramic radiograph will be reviewed by a member of research team prior to choosing which teeth (less than 10) will be to be tested.
	4)	Blood pressure, and heart rate values recorded at this appointment will be obtained from the medical record by a member of research team prior to the extraction.
	5)	The researcher initially will palpate the gum around selected teeth and record any discomfort
	6)	A plastic clip, pulse oximeter will be placed over the teeth, one at a time, to measure blood flow by measuring the presence of pulse in these teeth for approximately for 15-30 seconds per tooth.
Procedure	7)	The clip will remain on the tooth for additional 2-3 minutes to continually measuring pulse while the following tests are taken place:
		a. Cold Testing: This test is used to assess if the tooth is "dead" or "alive" by measuring sensation of cold from the tooth. A small cotton ball will be sprayed with cold spray (called Endo-Ice) and then placed on the surface of that tooth for approximately 15 seconds or till participant reports any sensation of cold. There would be 30 seconds wait time prior to the next step.
		b. Electrical Pulp Testing: This test is used to assess if the tooth is "dead" or "alive" by measuring sensation of electrical pulses from the tooth. A small probe attached to an electrical pulp testing (EPT) device will be placed on the surface of that tooth for approximately 15 seconds or till participant reports any tingling sensation. There would be 30 seconds wait time prior to the next step.
		c. Percussion Testing: This test is used to assess if the tooth is "dead" or "alive". The end of the mouth mirror is used to gently tap on the tooth surface and record any discomfort. There would be 30 seconds wait time prior to removal of the clip.

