 - **Percussion Testing:** This test is used to assess if the tooth is "dead" or "alive". The end of the mouth mirror is used to gently tap on the tooth surface and record any discomfort. There would be 30 seconds wait time prior to removal of the clip.
 - 0
- Once the tests above are completed, the plastic clip will be removed from your tooth. The pulse oximeter sensors will be removed from the plastic clip and replace with the LDF sensor. The plastic clip will be placed back over the teeth previously tested to measure the blood flow with the LDF. Blood flow will be measured by the presence of a pulse in each tooth for approximately for 15-30 seconds. Once the measurement is obtained, the plastic clip will be removed from the tooth.

- After obtaining participant's permission, researchers will obtain a de-identified copy of the participants dental radiographs
- After planned extraction is completed by the oral surgery provider, the tooth/teeth from the standard of care procedure will be provided to the researcher for further analysis to determine of the tooth is "alive or dead". This process will occur at the University of Michigan School of Dentistry Oral Surgery Clinics.
- Upon completion of extraction, the teeth will be placed in formalin-containing bottle. After formalin fixation, the teeth will be prepared for histological examination using 10% EDTA for demineralization. Following that, the teeth are trimmed, embedded in paraplast and cut longitudinally to obtain 6um thick section. The sections were stained with H&E and examined with a light microscope. The histological diagnosis are based on the classification used by Seltzer et al. as follow:
 - 1. Normal Pulp: Intact, uninflamed pulp
 - 2. Transitional Stage: Intact pulp with scattered inflammatory cells
 - 3. Pulpitis: inflammatory process affecting the coronal and radicular
 - 4. Pulp Necrosis: All pulp tissue is necrotic

STUDY ENROLLMENT AND WITHDRAWAL

1.6 **Subject Inclusion Criteria**

In order to be eligible to participate in this study, you must meet the following criteria:

- 1. Must be a patient of the University of Michigan School of Dentistry Oral Surgery Clinics
- 2. Must be scheduled for at least one tooth extraction at Oral Surgery Clinic
- 3. Must be 18 to 65 years old
- 4. Must be able to understand and willing to cooperate with all study procedures
- 5. Must be able to sign an IRB-approved written consent

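### Section 1.22 tests the oximeter against Cold/EPT with a paired t-test although the readings share no scale, and no accuracy measure is assigned to the oximeter

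*Combined protocol and SAP*

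**What the plan says.** Section 1.22 (Final Analysis Plan) opens with the aim "To compare accuracy of pulp vitality between traditional tooth vitality testing (Cold and EPT) to pulse oximeter reading", so as to decide whether the oximeter reliably indicates vitality. It then plans two analyses that set these readings against each other:

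- "We will analyze the relationships between these clinical readings using Pearson correlations and/or Chi Square tests"
- "Pulse oximeter reading will be compared against the gold standard (Cold and EPT) assessment using paired t-tests, 95% confidence intervals for the difference"

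The quantities are described elsewhere:

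- **Oximeter.** Section 1.5: "Measurements obtained from pulse oximeter gives a series of reading of oxygen saturation level, and pulse". The procedure lists in the Protocol Summary and Study Design instead say that the device is used "to measure blood flow by measuring the presence of pulse in these teeth".
- **Cold and EPT.** Study Design describes each as a stimulus applied for about 15 seconds or until the participant reports a sensation.
- **Form 2.** As extracted, it has one reading field per test, with no unit or code.

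Section 1.20 (Study Hypotheses) plans sensitivity, specificity and predictive values for heat, cold and EPT. It adds that clinical measurements of extracted teeth will be compared with histology, but gives no statistic or cut-off for that. The primary outcome in Section 1.5 is "Correlation Between Subjective and Objective Measurements of Pulpal Status".

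**The concern.** A paired difference means something only when both members of the pair measure the same quantity on the same scale. Saturation or pulse minus an EPT reading or a cold response is not such a difference. The text available gives no unit, coding, oximeter cut-off, rule for summarising the series of oximeter readings, or rule for combining Cold with EPT into one reference.

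A yes/no coding by presence of pulse is possible, but Section 1.22 does not adopt it. Even then, a paired t-test compares only the proportions positive; it does not ask whether the same teeth are positive.

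At stake is the question in the trial's title and in Aim 4. A non-significant result could be read as the oximeter matching the reference when the two disagree in most teeth, and a significant one as failure when they agree in nearly all. With no coding or cut-off fixed, one could also be chosen after the data are seen.

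**Working it through.** The plan has no figure of its own to reproduce on this point. Section 1.21 states 35 completers without derivation, and the argument does not depend on that number. All means, SDs and tables below are assumptions that show the logic, and teeth are treated as independent unless stated.

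**Number of teeth.** Section 1.6: "Must be scheduled for at least one tooth extraction at Oral Surgery Clinic". Section 1.5: "Pulse oximeter measurements would be used for teeth that are planned for extraction and also up to 2-5 additional teeth in each participant". With one extraction tooth and two to five others, the count runs from 35 × (1 + 2) = 105 to 35 × (1 + 5) = 210.

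**Raw readings.** With zero correlation, expected t = (difference in means) / √(SD₁² + SD₂²) × √n, where √105 = 10.247 and √210 = 14.491.

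| Oximeter, mean (SD) | EPT, mean (SD) | Difference / SD | t, n = 105 | t, n = 210 |
|---|---|---|---|---|
| SpO2 85 (8) | 35 (15) | 50 / 17.0 | 30.1 | 42.6 |
| Pulse 72 (10) | 35 (15) | 37 / 18.0 | 21.0 | 29.7 |
| SpO2 85 (8) | ×2: 70 (30) | 15 / 31.0 | 5.0 | 7.0 |
| SpO2 85 (8) | ×85/35 = 2.43: mean 85 | 0 | 0 | 0 |
| SpO2 85 (8) | ×3: 105 (45) | -20 / 45.7 | -4.5 | -6.3 |

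The mean difference is one mean minus the other, so shuffling the oximeter values across teeth leaves it unchanged.

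Ordinary recording choices have the same effect. In one simulated set of 35 teeth (each diseased with probability 0.4; SpO2 85 healthy, 75 diseased, SD 5; EPT 30 and 60, SD 10):

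- SpO2 in percent minus EPT is +40.7 (95% CI 33.2 to 48.1).
- SpO2 as a fraction minus EPT is -39.2 (-45.1 to -33.3).
- The Pearson correlation is -0.641 both times.

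**Yes/no coding, 105 teeth.** Here the mean difference = (oximeter-only positives − EPT-only positives) / n.

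| | Table (a) | Table (b) |
|---|---|---|
| Both +, oximeter only, EPT only, both − | 0, 30, 30, 45 | 30, 6, 0, 69 |
| Mean difference | 0 | 6/105 = 0.057 |
| Paired t, p | 0, 1.00 | 2.51, 0.014 |
| Agreement | 45/105 = 43% | 99/105 = 94% |
| Chance agreement | (30×30 + 75×75)/105² = 0.592 | (36×30 + 69×75)/105² = 0.567 |
| Kappa | -0.40 | 0.87 |
| Chi-square (uncorrected) | 16.8, p < 0.001 | 80.5, p < 0.001 |

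The t-test passes the table with disagreement in most teeth and flags the one with close agreement. The chi-square p-value does not separate them either. If the two tests agreed in every tooth, every difference would be zero and t would be undefined (0/0).

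**Precision of replacement measures.**

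- *AUC against histology*, assumed 0.80, with d diseased and h healthy teeth. Hanley–McNeil: SE² = [A(1−A) + (d−1)(Q₁−A²) + (h−1)(Q₂−A²)] / (d·h), where Q₁ = A/(2−A) = 0.667 and Q₂ = 2A²/(1+A) = 0.711. For 5/5, 10/10, 18/17 and 35/35, SE is 0.148, 0.102, 0.076 and 0.053; the 95% half-width (1.96 × SE) is 0.29, 0.20, 0.15 and 0.10.
- *Kappa in all tested teeth*, assumed 0.60 with 30% positive on each test. The large-sample SE is 0.086 (105 teeth) and 0.060 (210 teeth); half-width 0.17 and 0.12. With design effect 1 + (m−1) × ICC and an assumed ICC of 0.1 to 0.5, these widen to 0.18–0.24 (m = 3) and 0.15–0.22 (m = 6).

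**The case against.** The strongest reply is that the declared primary outcome is a correlation, which the Pearson/chi-square sentence covers, while histology is only exploratory and no clinical decision rests on the device. That is true, and it limits the defect to the accuracy aim. But Section 1.22 itself opens with that aim, and Aim 4 asks the same question.

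Second, Pearson's r on the two yes/no tables (phi) is -0.40 in (a) and +0.88 in (b), so a planned statistic would expose the disagreement. This stands as far as it goes. The plan's and/or leaves Pearson optional, however, and a correlation is still not an accuracy measure.

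Third, the tables are extreme, and multiplying EPT by 2 or 3 is not something the plan suggests. Both are illustrations only. In (b) the significant result does reflect a real difference in positive rates; the point is that this is a different question from accuracy. Recording saturation as a percentage or a fraction is no contrivance, and that alone reverses the sign.

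Fourth, the Protocol Summary and Section 1.1 show an intent to compare blood-flow measurements with histology. Agreed; what is missing is the statistic and the cut-off.

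Fifth, McNemar's test, in the next sentence of Section 1.22, also compares only positive rates. That sentence concerns clinical pulpal status against histology, does not name the oximeter and needs clarifying separately.

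Finally, the tooth count and precision are uncertain. The documents also mention ten teeth in total and fewer than ten, and the two to five additional teeth are an upper limit. With 35 histology teeth but 20% diseased (7/28), the AUC half-width is 0.21, not 0.15.

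**Conclusion.** The concern holds. As written, the paired t-test and its interval measure neither agreement nor accuracy. On raw readings the answer is set by the units, including its sign; on yes/no data it addresses only equality of positive rates. No accuracy statistic or cut-off is assigned to the oximeter anywhere in the text available, so the accuracy aim of Section 1.22 is unmet for the device under study.

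The logic does not depend on the assumed numbers. The sizes shown do: they rest on invented means, SDs and tables, and on independence between teeth. They are not forecasts for this trial. The primary correlation outcome is unaffected. The plan should be corrected before the data are analysed.

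**What to change.** 1. Delete the paired t-test and the interval for the difference from Cold/EPT.
2. State whether the oximeter reading is SpO2, pulse rate or presence of pulse, and how the series is summarised. State the unit and direction of the EPT reading.
3. In all tested teeth, keep the planned Pearson/chi-square. Add percent agreement and kappa with 95% CI under a yes/no coding fixed before analysis, or the AUC of the oximeter reading against the Cold response and the EPT response separately. Call these concordance, since Section 1.20 takes histology as the true status.
4. In extracted teeth with histology, report the oximeter's AUC with 95% CI. Extend the Section 1.20 measures to the oximeter at a cut-off or pulse-present rule fixed before analysis. If none can be fixed, report the AUC and label any data-derived cut-off exploratory.
5. Two related details are worth settling at the same time: which Section 1.20 category the Transitional histology class joins, and participant-clustered intervals (cluster bootstrap or clustered SE) where one person contributes several teeth.

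The cost is SAP wording, a coding or cut-off that the investigators must supply because the documents give none, and modest programming. No new procedures or data are needed. The drawback is precision against histology: Section 1.31 limits it to extracted teeth that meet the inclusion criteria, their number is not stated, and some participants may contribute none.
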